AST	Aspartate transaminase
ATC	Anatomical Therapeutic Chemical
BP	Blood pressure
CI	Confidence interval
CR	Complete response
CSP	Clinical study protocol
CSR	Clinical study report
CT	Computerized tomography scan
CTCAE	Common Terminology Criteria for Adverse Events
DCO	Data cut-off
DCR	Disease control rate
DNA	Deoxyribonucleic acid
DoR	Duration of response
ECG	Electrocardiogram
eCRF	Electronic case report form
EGFR	Epidermal growth factor receptor
EGFRm+	EGFR mutation positive
FAS	Full Analysis Set
HIV	Human immunodeficiency virus
IP	Investigational product
IVRS	Interactive Voice Response System
KM	Kaplan-Meier
L858R	An amino acid substitution at position 858 in EGFR, from a Leucine (L) to an Arginine (R)

Abbreviation or special term	Explanation
LD	Longest diameter
LDH	Lactate dehydrogenase
LLoQ	Lower limit of quantification
LVEF	Left ventricular ejection fraction
MedDRA	Medical Dictionary for Regulatory Activities
MRI	Magnetic resonance imaging
MUGA	Multi-gated acquisition scan
N/A	Not applicable
NE	Not evaluable
NSCLC	Non-small cell lung cancer
NTL	Non-target lesion
OAE	Other significant adverse event
ORR	Objective response rate
OS	Overall survival
PD	Progression of disease
PD-L1	Programmed Death Ligand 1
PFS	Progression Free Survival
PID	Percentage intended dose
PK	Pharmacokinetics
PR	Partial response
PT	Preferred term
QD	Once daily
RDI	Relative dose intensity
RECIST	Response Evaluation Criteria in Solid Tumors
SAE	Serious adverse event
SD	Stable disease
SLD	Sum of longest diameter
SOC	System organ class
T790M	An amino acid substitution at position 790 in EGFR, from a Threonine (T) to a Methionine (M)

Abbreviation or special term	Explanation
T790M-	T790M mutation negative
T790M+	T790M mutation positive
TKI	Tyrosine kinase inhibitor
TL	Target lesion
ULoQ	Upper limit of quantification
WHO	World Health Organization

AMENDMENT HISTORY

Date	Brief description of change
21 st August 2017	To reflect changes documented in Protocol Version 2.0 02-Mar-2017.

1. STUDY DETAILS

1.1 Study objectives

Primary objective

Objective:	Outcome Measure:
To investigate the safety and tolerability profile of AZD9291 in combination with MEDI4736.	Adverse events (graded by Common Terminology Criteria for Adverse Events (CTCAE v4)) Clinical chemistry, haematology and urinalysis Vital signs (pulse and blood pressure), Physical Examination, Weight Digital Electrocardiogram (ECG) Echocardiogram/Multi Gated Acquisition Scan (MUGA) (for Left Ventricular Ejection Fraction) WHO Performance Status

Exploratory objectives

Objective:	Outcome Measure:
To assess the safety and tolerability of AZD9291 as a single agent	Adverse events (graded by CTCAEv4) Clinical chemistry, haematology and urinalysis Vital signs (pulse and blood pressure), Physical examination, Weight Centrally reviewed digital Electrocardiogram (ECG) Echocardiogram/Multi gated Acquisition Scan (MUGA) (for left ventricular Ejection fraction) WHO performance status Serious Adverse events (graded by CTCAEv4)

Objective:	Outcome Measure:
To obtain a preliminary assessment of the efficacy of AZD9291 in combination with MEDI4736 and AZD9291 monotherapy	Objective Response Rate (ORR) Progression Free Survival (PFS) landmark at 6 and 12 months Overall Survival (OS) landmark at 12 months Duration of Response (DoR) Disease Control Rate (DCR) Tumour shrinkage using Investigator assessments according to RECIST 1.1
To assess the PK of AZD9291 as a single agent and in combination with MEDI4736.	Plasma concentrations of AZD9291 and metabolites AZ5104 and AZ7550.
To characterise the PK and immunogenicity of MEDI4736 after single dosing and at steady state after multiple dosing when given intravenously to patients with EGFRm non small-cell lung cancer (NSCLC) in combination with AZD9291	Plasma concentrations of MEDI-4736 to characterise PK Blood samples for anti-drug antibodies (ADA) to characterise immunogenicity.
The following exploratory objectives may be reported separately from the main Clinical Study Report (CSR) and will not be covered in this Statistical Analysis Plan.	
To characterise the pharmacodynamics of MEDI4736 after single dosing and at steady state after multiple dosing when given intravenously to patients with EGFRm non small-cell lung cancer (NSCLC) in combination with AZD9291	Blood samples for soluble PD-L1 to characterise pharmacodynamics .
To investigate the relationship of response and PFS in patients who are PD-L1 positive and those that are PD-L1 negative.	Retrospective evaluation of baseline PD-L1 expression in tumour (based on immunohistochemistry assessment).
To collect and store deoxyribonucleic acid (DNA) for future exploratory research into genes/genetic variation that may influence PK or response AZD9291 as a single agent and in combination with MEDI4736 (i.e. absorption, distribution, metabolism, excretion, safety and efficacy) and/or susceptibility to/development of cancers.	Correlation of polymorphisms with variation in Pharmacokinetics (PK), pharmacodynamics, safety or response observed in patients treated with AZD9291 as a single agent and in combination with MEDI4736.

Objective:	Outcome Measure:

To collect and store tumour samples and blood-based (plasma and serum) samples for potential exploratory research into factors that may influence susceptibility to/development of NSCLC/cancer and/or AZD9291 as a single agent and in combination with MEDI4736 (where response is defined broadly to include efficacy, tolerability or safety).
	
Collection of tumour and blood-based samples to include, but not be limited to, investigation of biomarkers such as Epidermal growth factor receptor (EGFR) mutations (T790M, L858R, etc). These samples may be shared with a diagnostic partner for development of a companion diagnostic if needed. The samples may also be used to investigate the relationship between PK and blood-borne biomarkers.
 
Samples may be analysed retrospectively. Any biomarker data generated may be reported separately and may also form part of a pooled analysis with other AZD9291 studies.

1.2 Study design

This trial was initially designed as a phase III, multi-centre, open label, randomized study to assess the efficacy and safety of AZD9291 (80 mg, orally, once daily) in combination with MEDI4736 (10 mg/kg, IV infusion every 2 weeks [q2w]) versus AZD9291 monotherapy (80 mg, orally, once daily) in patients with a confirmed diagnosis of EGFR T790M mutation positive (T790M+) locally advanced or metastatic NSCLC (Stage IIIB-IV), who have progressed following prior therapy with an approved EGFR-TKI agent.

All patients must have documented radiological progression on EGFR-TKI treatment and on the last treatment administered prior to enrolling in the study.

A mandatory biopsy was needed for central testing of T790M mutation status following confirmed disease progression on previous treatment.

Three hundred fifty patients were planned to be randomized, however recruitment was stopped after enrolling 29 patients. Early termination of enrolment into the study was decided in the light of a higher than anticipated incidence of interstitial lung disease-like events in patients receiving the combination of AZD9291 with MEDI4736 in a separate multi-arm Phase 1b open label study D5160C00006 (TATTON).

Two summaries of the study data are planned:

Primary Summary

A primary summary will be performed with a data cut-off date representative of when the last country with active patients receives ethics and regulatory approval for protocol version 2.0. This summary will be used for the CSR and will report data according to the randomised or actual treatment groups as specified in [Section 2](#).

Final Summary

Patients had been initially randomized to receive either AZD9291 in combination with MEDI4736 or AZD9291 monotherapy. Depending on the treatment being received, the patients will be categorized as follows for the purpose of delineating the required study plan and assessments:

GROUP A - Patients on AZD9291 monotherapy

Group A includes patients continuing to receive AZD9291 monotherapy following data cut-off (DCO) for the primary analysis, who were either randomised to receive AZD9291 monotherapy or were randomised to receive AZD9291 in combination with MEDI4736 but who have discontinued MEDI4736 and been followed up for 90 days post discontinuation of MEDI4736

Patients may continue dosing with the drug according to the protocol as long as they are continuing to show clinical benefit, as judged by the Investigator, and in the absence of a discontinuation criterion. These patients have no pre-scheduled visits until treatment discontinuation (apart those needed for the drug accountability and dispensing) and will follow the normal clinical site approach. Following approval of clinical study protocol (CSP) version 2.0 at the site only SAE, outcomes of pregnancy and drug dispensing/ accountability data will be collected for Group A patients. This may result in sparse data in some of the summaries in the primary summary.

GROUP B - Patients on MEDI4736 in combination with AZD9291 or MEDI4736 monotherapy

Group B includes patients randomised to receive MEDI4736 and AZD9291 and who are continuing to receive MEDI4736 either in combination with AZD9291 or as a monotherapy

Patients may continue treatment with MEDI4736 monotherapy or in combination with AZD9291 as long as they are continuing to show clinical benefit, as judged by the Investigator, and in the absence of a discontinuation criterion. Group B patients should follow the schedule / assessments specified in the CSP. Group B patients that discontinue MEDI4736 during the study can be switched to Group A and follow the AZD9291 Monotherapy assessment schedule following completion of the 90 day safety follow up. Following approval of CSP version 2.0

The overall study design is shown in Figure 1 below. The study schedule for Group A and Group B subjects is detailed in Tables 1 and 2 of the CSP, respectively.

[figure not shown]
A final addendum summary will be performed when the last patient discontinues MEDI4736 and completes their required safety follow up. All outputs from the primary summary will be repeated at the final summary, except those relating to change in tumour size at 6 weeks, which will have been fully reported during the primary analysis. Only data collected between

the primary summary data cut-off and the time when last patient receiving MEDI4736 reaches the end of safety follow up, will be summarised. If three or fewer patients are included in this summary, then only listings will be produced, with no summary tables.

If all patients have discontinued from MEDI4736 treatment at the time of DCO for the primary study summary, the primary summary will be the only summary of data for the study.

Final summary will show data summarized by Group A and Group B as defined above. For demography, exposure and SAEs data will be summarized for both Groups A and B. Other data will be reported for Group B only. Patients that do not meet criteria for either Group A or Group B definition will be listed along with any relevant data that has been collected.

Figure 1 Study flow chart

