2. ANALYSIS SETS

2.1 Definition of analysis sets

These analysis sets apply only to the primary summary. The final summary will include only data collected between the primary summary data cut-off and the time when last patient receiving MEDI4736 reaches the end of safety follow up.

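### The final summary repeats survival landmarks timed from randomisation in Group B, a group identified by still being on MEDI4736, so its 12-month OS contains guaranteed survival time; the post-cut-off data rule also conflicts with the outputs to be repeated

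*SAP*

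**What the plan says.** Section 1.2 plans a primary summary, used for the CSR, with a "data cut-off date representative of when the last country with active patients receives ethics and regulatory approval for protocol version 2.0". It then adds: "A final addendum summary will be performed when the last patient discontinues MEDI4736 and completes their required safety follow up". On content it says "All outputs from the primary summary will be repeated at the final summary, except those relating to change in tumour size at 6 weeks". The 12-month OS estimate (OS12), the 6- and 12-month PFS estimates and the KM plots are not among the exceptions.

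On who is reported, section 1.2 says "For demography, exposure and SAEs data will be summarized for both Groups A and B" and then "Other data will be reported for Group B only". Efficacy is therefore a Group B output, and section 4.1 confirms that final summaries are presented by Group A and Group B. The definition reads: "Group B includes patients randomised to receive MEDI4736 and AZD9291 and who are continuing to receive MEDI4736", either with AZD9291 or alone.

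On which data are used, section 2.1 limits the analysis sets to the primary summary and continues: "The final summary will include only data collected between the primary summary data cut-off and the time when last patient receiving MEDI4736 reaches". The window closes when that patient's safety follow-up is complete. Section 1.2 gives the same window.

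On size, section 1.2 says "If three or fewer patients are included in this summary, then only listings will be produced, with no summary tables". There is no final summary at all if everyone has stopped MEDI4736 by the DCO.

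Sections 3.2.1 and 3.2.7 time PFS and OS from randomisation and define the landmarks as KM estimates. Neither gives a delayed-entry rule or a new time origin for the final summary.

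**The concern.** A patient can be in Group B only by living long enough to still be on MEDI4736 when the group is formed. Combination-arm patients who died earlier are not in it. If survival is then counted from randomisation, the stretch from randomisation to the DCO contains no deaths by construction, and an ordinary KM curve credits that stretch as observed survival. Group B OS12 would then describe how the group was chosen as much as how patients on the combination fared.

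The second difficulty is internal. The outputs to be repeated depend on information that predates the DCO, while the stated window admits only later data. A programmer cannot satisfy both instructions, and the choice made would change the PFS, response and duration results.

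At stake is an addendum table showing an inflated, possibly perfect, 12-month survival for a combination whose enrolment was stopped because of a safety signal in another study.

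**Working it through.** The SAP states no OS12, event or survival figure on this point, so there is none to reproduce.

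**1. Guaranteed survival time**

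Inputs from the SAP: time origin is randomisation (3.2.7); the estimator is KM at 12 months (3.2.7); a month is 30.4375 days (4.1), so 12 months is 12 × 30.4375 = 365.25 days; OS time is date minus randomisation date plus 1 (3.2.7). The SAP gives no randomisation dates, calendar DCO or survival rate.

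Let S be the true survival curve and t0 the time from randomisation to DCO. Among patients selected only for being alive at t0:

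- if t0 < 12 months, KM from randomisation targets S(12)/S(t0), which exceeds S(12) whenever S(t0) < 1;
- if t0 ≥ 12 months for every member, nobody can have died by month 12, so the estimate is exactly 100%.

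For exponential survival, S(12)/S(t0) = S(12)^(1 − t0/12). At an assumed true OS12 of 70%, t0 = 3 gives 0.70^0.75 = 0.765; t0 = 6 gives 0.70^0.50 = 0.837; t0 = 9 gives 0.70^0.25 = 0.915. Over a range of assumed values:

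| Assumed true OS12 | t0 = 3 | t0 = 6 | t0 = 9 | t0 ≥ 12 |
|---|---|---|---|---|
| 50% | 59.5% | 70.7% | 84.1% | 100% |
| 60% | 68.2% | 77.5% | 88.0% | 100% |
| 70% | 76.5% | 83.7% | 91.5% | 100% |
| 80% | 84.6% | 89.4% | 94.6% | 100% |

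The exponential shape is not essential. At t0 = 6 and a true 70%, Weibull shapes of 0.7 and 1.5 give 0.872 and 0.794, against 0.837.

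One date helps with timing. The SAP's amendment history dates protocol version 2.0 at 02-Mar-2017, and the DCO is tied to approval of that version, so it should not fall before then. A member randomised on or before 02-Mar-2016 would have at least 365 + 1 = 366 days of OS time at the DCO, above 365.25. Whether any member was randomised that early is not in the SAP.

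**2. PFS landmarks**

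A Group B member cannot have died before the DCO, so that part of the PFS event is excluded. Progression before the DCO is not excluded: section 3.1 provides for Group B patients who continue MEDI4736 after progression.

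**3. The data window against the repeated outputs**

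| Repeated output | Needs from before the DCO |
|---|---|
| Demography | Baseline data |
| OS, PFS | Randomisation date; first progression for PFS |
| ORR, DCR, tumour shrinkage | Baseline sum; nadir and earlier progression for visit responses |
| DoR | Date of first response |
| Total and actual exposure (3.3.7) | First-dose date, earlier interruptions |
| RDI, PID (3.3.8) | Earlier cumulative dose |

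Demography is explicitly required, so the window cannot be meant with full literalness. Applied literally, it would drop first progressions and first responses that occurred before the DCO.

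**4. Do the size rules prevent the tables?**

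The listings-only rule counts patients included in the summary, and Group A is included for some outputs. As worded, 1 Group B patient plus 3 Group A patients makes 4, which exceeds three, so Group B efficacy tables could follow. The rule in section 4.1.3 requiring 10 subjects in a group governs visit-based statistics only, not KM, OS12, ORR or DCR.

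**The case against.** **Group B carries no date.** Only the Group A definition names the DCO, and section 1.2 introduces the groups to set visit schedules and lets patients move from B to A. This stands in part: DCO status is a strong inference, not the only possible reading. It is supported by the Group A wording, the post-DCO window and the condition that someone be on MEDI4736 at the DCO. If status at approval of protocol version 2.0 were meant, survival to that date would be guaranteed instead.

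**The direction is not certain for every timing.** This stands. A reader might infer that the reported figure must be too high whatever the DCO. The inequality concerns what is being estimated, and under selection on being alive only. Group B is also selected on remaining on MEDI4736, which the algebra does not sign. An observed value can also fall either way: with 4 members fully followed, one death between DCO and month 12 gives 75%. Only the case of every t0 being at least 12 months is certain.

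**The SAP does have a data rule.** This stands too. A reader might infer that the SAP is silent on earlier data, but sections 1.2 and 2.1 admit post-DCO data only. The fault is that this rule cannot be reconciled with the outputs it is applied to.

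**Section 4.2.7 puts all efficacy in the FAS.** This does not rescue the final summary, because section 2.1 confines the analysis sets to the primary summary and section 1.2 assigns efficacy to Group B.

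**Little depends on it.** Largely true. OS12 by randomised arm is already in the primary summary, no hypothesis is tested, and the addendum may never be produced or may be listings only.

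**Conclusion.** The point holds as a minor one. Followed as written, the SAP produces a Group B OS12 timed from randomisation in patients who had to be alive when the group was formed. It is exactly 100% if every member was randomised at least 12 months before the DCO. For shorter intervals it targets a value above the true OS12 under selection on survival alone; the 6.5, 13.7 and 21.5 point excesses at 3, 6 and 9 months (true 70%, exponential) are illustrations, not estimates for this trial. The conclusion rests on reading Group B membership as status at the DCO.

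The conflict between the post-DCO window and the repeated endpoints is separate and needs no distributional assumption.

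Two stronger inferences are not supported. The primary summary and the CSR are not affected, since they report efficacy for all randomised patients by randomised arm. The PFS landmarks do not carry guaranteed freedom from progression, because treatment may continue after progression.

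**What to change.** - **Outputs.** In section 1.2, add the PFS, OS, ORR, DoR, DCR and tumour-shrinkage tables and the KM plots to the outputs not repeated at the final summary, and list Group B efficacy data only. If tables are wanted, produce them cumulatively from randomisation in the FAS by randomised arm, and adjust section 2.1 to allow this.
- **Reporting group.** State that Group A or B for the final summary is fixed by status at the primary DCO, including for patients who later switch from B to A.
- **Data window.** In sections 1.2 and 2.1, state that the window selects which records are reported, while randomisation date, baseline, nadir and earlier response and progression are kept from before the DCO for the listings.
- **Exposure.** State whether exposure, RDI and PID are cumulative, using all dosing records, or post-DCO only, using only post-DCO dosing, and do not mix the two.

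The listing option costs a few sentences and leaves fewer addendum tables. The cumulative FAS option keeps the tables, at the price of an exception to the Group A/B layout.

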3.3.1 Adverse Events

All AEs will be coded using the latest version of the Medical Dictionary for Regulatory Activities (MedDRA) and graded according to the National Cancer Institute CTCAE (version 4.0.3 or later).

Preferred terms used to identify adverse events of special interest (AESI) will be listed before database lock and documented in the Study Master File. Groupings of certain MedDRA preferred terms will be based on preferred terms provided by the medical team and a listing of the preferred terms in each grouping will be produced.

The grouped preferred terms for AESI for AZD9291 are shown below. A separate list will be produced for MEDI 4736. The individual preferred terms will be available in the programming specification documentation:

- Ocular surface effects
- Dry eye/conjunctivitis
- Interstitial lung disease and acute interstitial pneumonitis
- Nail and nail bed conditions
- Skin disorders including dermatitis
- Upper GI tract inflammatory events
- Cardiotoxicity
- Diarrhoea

- Colitis/Enterocolitis (Gastrointestinal Disorder)
- Hepatitis/ Hepatic Toxicity (Hepatic Function Abnormality)
- Infusion-related Reactions
- Anaphylaxis and Serious Allergic Reactions (Hypersensitivity)
- Neuromuscular Toxicity/Neuropathy
- Endocrinopathy

Any AE occurring before study treatment will be included in the data listings but will not be included in the summary tables of AEs.

Any AE occurring within 30 days of discontinuation of AZD9291 and within 90 days for MEDI4736 will be included in the AE summaries. Any events in this period that occur after a subject has received further therapy for cancer (following discontinuation of AZD9291) will be flagged in the data listings. If AZD9291 is discontinued less than 60 days after MEDI4736, subjects should be followed up to 90 days from the date of MEDI4736 discontinuation.

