4.2.8.1 Adverse events

All AEs, both in terms of MedDRA PT and CTCAE grade, will be listed and summarized descriptively by count (n) and percentage (%) for each treatment group. MedDRA will be used for coding. Any AE occurring before study treatment (i.e., before Study Day 1) will be included in the AE listings, but will not be included in the summary tables (unless otherwise stated). These will be referred to as 'pre-treatment'. The summary tables will include all AEs that occurred after the start of treatment up until the end of the follow-up period.

All reported AEs will be listed along with the date of onset, date of resolution (if AE is resolved), investigator's assessment of severity and relationship to study drug. Frequencies and percentages of subjects reporting each preferred term will be presented (i.e., multiple events per subject will not be accounted for apart from on the episode level summaries).

Summary information (the number and percent of subjects by treatment) will be tabulated for:

- All AEs
- All AEs causally related to study treatment

- AEs with CTCAE grade 3 or higher
- AEs with CTCAE grade 3 or higher, causally related to study treatment
- Fatal AEs
- All SAEs
- AEs leading to discontinuation
- OAEs

An overall summary of the number and percentage of subjects in each category will be presented, as will an overall summary of the number of episodes in each category. In addition, a truncated AE table of the most common AEs, showing all events that occur in at least 5% of subjects overall will be summarized by preferred term, by decreasing frequency. This cut-off may be modified after review of the data.

AEs will be assigned CTCAE grades and summaries of the number and percentage of subjects will be provided by maximum reported CTCAE grade, SOC, PT and actual treatment group.

In addition, AEs with an outcome of death, SAEs, and OAEs will be listed.

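### The rule that drops the final summary requires only that MEDI4736 has stopped, not that its safety follow-up is complete, so adverse events after the cut-off could fall in no planned output

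*SAP*

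**What the plan says.** SAP Section 1.2 plans a primary and a final summary. The primary summary has a "data cut-off date representative of when the last country with active patients receives ethics and regulatory approval for protocol version 2.0". For the final one, "A final addendum summary will be performed when the last patient discontinues MEDI4736 and completes their required safety follow up". Two paragraphs later comes the waiver: "If all patients have discontinued from MEDI4736 treatment at the time of DCO for the primary study summary", then "the primary summary will be the only summary of data for the study".

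Two sections set the AE reporting window. Section 3.3.1 says "Any AE occurring within 30 days of discontinuation of AZD9291 and within 90 days for MEDI4736 will be included in the AE summaries". Section 4.2.8.1 says "The summary tables will include all AEs that occurred after the start of treatment up until the end of the follow-up period".

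The final summary is organised by Group A and Group B, both defined in Section 1.2. A patient randomised to the combination enters Group A as one of those "who have discontinued MEDI4736 and been followed up for 90 days post discontinuation of MEDI4736". Group B holds those "who are continuing to receive MEDI4736 either in combination with AZD9291 or as a monotherapy". Section 1.2 also provides that patients who fit neither definition are listed with whatever relevant data were collected. That provision is part of the final summary.

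**The concern.** The trigger and the waiver should be complements: the final summary should be dropped only when nothing is left for it to report. They are not. The trigger needs two events, MEDI4736 stopped and follow-up completed; the waiver looks only at the first. A patient who is off MEDI4736 but still in follow-up at the cut-off satisfies the waiver while still having reportable AE time to come.

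The subject is the primary objective. Section 1.1 makes the safety and tolerability of the combination the sole primary objective, and the separate 90-day window shows that the plan regards late events after MEDI4736 as reportable. Interstitial lung disease is a listed AE of special interest, and enrolment stopped because of such events with this combination in a separate study. A gap in planned reporting of the period just after MEDI4736 therefore matters, even in a purely descriptive report.

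**Working it through.** The plan gives no figure to reproduce. The check compares the stated conditions and then counts days.

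**1. Trigger against waiver (Section 1.2)**

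| Status of the last patient at the primary cut-off | Trigger implies | Waiver implies |
|---|---|---|
| Still on MEDI4736 | Final summary to come | Does not apply; final summary to come |
| Off MEDI4736, follow-up not complete | Final summary to come | **No final summary** |
| Off MEDI4736, follow-up complete | Nothing left to wait for | No final summary |

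The rules conflict only in the middle row.

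**2. Does anything align the cut-off with the end of follow-up?** No. The primary cut-off follows the last country's approval of protocol version 2.0, an administrative date with no link to any patient's last MEDI4736 dose.

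**3. Does another output catch these patients?** On the definitions, a patient off MEDI4736 for fewer than 90 days is not in Group B (no longer receiving it) and not in Group A (90 days not yet completed). The listing for patients in neither group would cover them, but it belongs to the final summary and goes when that is waived. Section 1.2 also says that Group B patients who stop MEDI4736 can switch to Group A after the 90 days, which might be read as keeping them in Group B until then. That does not help either, since Group B is also reported only in the final summary.

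**4. Size per patient.** Let k be the number of days from stopping MEDI4736 to the primary cut-off. With the 90-day window of Section 3.3.1, the part after the cut-off is 90 − k days for 0 ≤ k < 90, and 0 otherwise.

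| k (days) | Days of the window in no planned output |
|---|---|
| 0 | 90 |
| 30 | 90 − 30 = 60 |
| 60 | 90 − 60 = 30 |
| 89 | 90 − 89 = 1 |
| 90 or more | 0 |

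**5. Number of patients.** Not computable: the SAP gives no MEDI4736 stop dates and no cut-off date.

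**6. After the fix.** If the waiver also required completed follow-up, it could apply only when k ≥ 90 for every patient who completes the 90 days, and the unreported part would be 0 days.

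**The case against.** The strongest reply is that the gap is conditional and the loss small. It needs every patient to be off MEDI4736 at the cut-off and at least one of them to be within 90 days of stopping. Reporting is descriptive, with no hypothesis testing (Section 4), on 29 patients, and no estimate in the primary summary depends on the waiver. With three or fewer patients the addendum would be listings only. All of this stands. It limits the size of the point but does not reconcile the two rules.

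One might also say that discontinuation was meant to include follow-up. The text does not support that: the trigger sentence in the same section names the two as separate events.

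Two stronger readings are tempting, and neither is supported.

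- A reader might infer that the late events would never be reported. The SAP shows only that no output planned in it would carry them. Section 3.3.1 still foresees follow-up to 90 days after MEDI4736, so an output is lost, not the data collection, and safety reporting outside this SAP cannot be judged from it.
- A reader might infer that the combination arm's AE rates are biased downward by a definite amount. With an assumed 14 or 15 of the 29 patients in that arm, one patient is 1/15 = 6.7% to 1/14 = 7.1%, about 7 percentage points. But the final summary covers only data after the primary cut-off (Sections 1.2 and 2.1) and is presented by Group A and Group B (Section 4.1), so the primary rates by arm would be the same with or without it. Moreover, the AE tables count subjects per preferred term (Section 4.2.8.1), so a late event need not change a count. The ILD-like events that ended enrolment arose in a separate study and are not evidence of missed events here.

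**Conclusion.** The point holds as an internal contradiction in the reporting rules. The waiver in Section 1.2 can remove the only planned output for AEs that Sections 3.3.1 and 4.2.8.1 say will be in the summaries. The loss is 90 − k days of the window for each patient who stopped MEDI4736 k < 90 days before the primary cut-off, and it arises only if all patients are off MEDI4736 at that date. The number of such patients is unknown and may be zero.

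What would be missing is a short listing or summary of late events, not a correction to the AE rates in the primary summary. The conclusion rests on reading discontinuation and completed follow-up as two events, as the trigger sentence does. It deserves correction because it concerns the primary objective and the remedy is specific and cheap.

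**What to change.** 1. Reword the waiver in Section 1.2 along these lines: *the primary summary is the study's only summary if, at its cut-off, every patient has both stopped MEDI4736 and completed the required safety follow-up.* Otherwise the addendum is produced, with patients in neither Group A nor Group B listed as Section 1.2 already foresees.
2. To meet Sections 3.3.1 and 4.2.8.1 in full, state that AEs after the cut-off and inside the MEDI4736 window are attributed to the combination, for example in a cumulative AE listing or table by actual treatment. The first change alone yields only a listing outside the treatment arms.

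The cost is one clause in the waiver and one sentence on attribution. At worst it adds a short addendum, listings only if three or fewer patients are included, from follow-up that the plan already foresees.
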